9.2 Extent of Exposure

Only subjects enrolled in this study may be treated with ¹²⁴I-AT-01. During the study, qualified clinical site staff will administer all study drug. The date and time for each dose will be recorded in the CRFs.

The actual dose of ¹²⁴I-AT-01 will be summarized in mCi and mg by study visit. The administration type (infusion, IV bolus), duration of administration (for infusions) and number of subjects experiencing an administration interruption and associated reason for interruption will be summarized by study visit.

 124 AT-01 compliance is defined as receiving 1 mCi (+/- 10%) (<= 2mg 124 AT-01). KI compliance is defined as receiving KI orally for 3 days in the specified time periods. The number of and percent of compliant subjects for 124 AT-01 and for KI will be summarized by visit.

A listing of all administrations of ¹²⁴I-AT-01 will be provided by subject and visit.

A listing of all administrations of potassium iodide (KI) will be provided by subject and visit.

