9.3 Adverse Events

Adverse events will be coded using the Medical Dictionary for Regulatory Activities (MedDRA) Version 24.1 to identify the system organ class and preferred term. All AEs and SAEs will be recorded from the time of informed consent until the final EOS telephone follow-up (~Week 10).

Treatment-emergent AEs are defined as events that are newly reported or reported to worsen in severity after the start of treatment. Adverse events that occur after the treatment start date, occur on the treatment start date with a time that is equal to or after treatment start time, or that have a missing AE start date will be categorized as treatment-emergent. Treatment-emergent AEs will be summarized for the Safety Set.

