9.4.1 TEAEs on Day of Dosing

Infusion-related reactions (IRRs) can be any signs or symptoms experienced by subjects during the infusion of pharmacologic or biologic agents or any event occurring on the first day of the infusion. Treatment-emergent adverse events starting on the day of dosing at each dosing visit will be summarized by SOC and PT in order to evaluate potential IRRs.

A data listing of TEAEs starting on the day of dosing at each dosing visit will be provided.

IRRs which occur during administration will be captured on the AT01 Infusion CRF as any non-blank answer for "If discontinued, provide reason" or "If interrupted, reason for interruption" and will be provided in a listing.

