9.4.2 TEAEs by Visit

TEAEs by CTCAE grade, treatment-emergent SAEs by CTCAE grade, and TEAEs leading to study withdrawal will be categorized by their start date. The two time categories will be (1) after Visit 1 and prior to the Visit 2 date and (2) after the Visit 2 date.

Page 23 of 38

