9.6 Vital Signs

Baseline and all post-baseline visit values and change from baseline to post-baseline values in systolic blood pressure, diastolic blood pressure, heart rate, weight, and body mass index (BMI) will be summarized for the Safety Set using descriptive statistics, as described in Section 4. Height at baseline will be summarized using descriptive statistics, as described in Section 4, and will be used in the calculation of BMI at post-baseline visits.

Vital sign results by visit will be presented in a data listing for subjects in the Safety Set.

Vital signs with clinically significant changes will be summarized and listed as 'flagged' based on the Sponsor's internal guidelines based on Appendix 14.3.

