14.3 Clinically Significant Change in Laboratory Values and Vital Signs

Category	Measurement	Criteria for Clinically Significant Change
Laboratory	Hematocrit (%)	Decrease > 20% and < LLN
_		<pre>Increase > 20% and > ULN</pre>
Laboratory	Hemoglobin (g/dL)	Decrease > 20% and < LLN
_		<pre>Increase > 20% and > ULN</pre>
Laboratory	Leukocytes (x109/L)	Decrease > 20% and < LLN
		<pre>Increase > 50% and > ULN</pre>
Laboratory	Lymphocyte count $(x10^9/L)$	Decrease > 20% and < LLN
		<pre>Increase > 50% and > ULN</pre>
Laboratory	Neutrophils $(x10^9/L)$	Decrease > 20% and < LLN
		Increase > 50% and > ULN
Laboratory	Platelets (x10 ⁹ /L)	Decrease > 20% and < LLN
		Increase > 50% and > ULN
Laboratory	Glucose (mmol/L)	Value < 2.775 mmol/L
		Increase > 50% and > ULN
Laboratory	Bilirubin (umol/L)	Increase > 50% and > ULN
Laboratory	Alkaline phosphatase (IU/L)	Increase > 50% and > ULN
Laboratory	Aspartate Aminotransferase (IU/L)	Increase > 100% and > ULN
Laboratory	Alanine Aminotransferase (IU/L)	<pre>Increase > 100% and > ULN</pre>
Laboratory	Potassium (mmol/L)	Absolute decrease $>$ 0.8 mmol/L and $<$
		LLN
		Absolute increase > 0.8 mmol/L and >
		ULN
Laboratory	Sodium (mmol/L)	Absolute decrease > 0.8 mmol/L and <
		LLN
		Absolute increase > 0.8 mmol/L and >
		ULN
Vital Signs	Systolic Blood Pressure (mmHg)	Decrease > 20 mmHg and SBP < 90 mmHg
Vital Signs	Diastolic Blood Pressure (mmHg)	Increase > 10 mmHg and DBP < 50 mmHg

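### Two SAP safety-reporting rules fail as written: the diastolic flag pairs a rise with a low limit, and the by-visit TEAE split omits the second dosing day

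*SAP*

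**What the plan says.** **Diastolic flag.** SAP 9.6 states that "Vital signs with clinically significant changes will be summarized and listed as" flagged, using Appendix 14.3. In that appendix the systolic criterion is "Decrease > 20 mmHg and SBP < 90 mmHg". The diastolic criterion directly below it is "Increase > 10 mmHg and DBP < 50 mmHg". The output is Table 14.3.4.2.

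**TEAEs by visit.** SAP 9.4.2 covers three items: TEAEs by CTCAE grade, and, in its words, "treatment-emergent SAEs by CTCAE grade, and TEAEs leading to study withdrawal will be categorized by their start date". The two time categories are "1) after Visit 1 and prior to the Visit 2 date and (2) after the Visit 2 date". The output is Table 14.3.2.3, whose title mentions no exclusion of dosing days.

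Two neighbouring sections bear on this. SAP 9.3 counts as treatment-emergent those events that "occur on the treatment start date with a time that is equal to or after treatment start time". SAP 9.4.1 provides that TEAEs "starting on the day of dosing at each dosing visit will be summarized by SOC and PT", with output in Tables 14.3.2.1 and 14.3.2.2.

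**The concern.** The diastolic row asks for a rise and a low result together. If programmed as written, the diastolic part of Table 14.3.4.2 will be close to empty whatever the data show, and a reader could take that as evidence of no clinically significant diastolic change. Change in vital signs is a named secondary endpoint. Blood pressure is measured 5-10 minutes after each dose, and Protocol 7.1.1.1 lists hypotension among the symptoms suggesting an infusion-related reaction. The flag cannot see the direction of change that the protocol itself watches for.

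The by-visit split exists to show what happens after the first dose and after the second, yet it leaves out the day of the second dose. Two other rules can place events on that day:

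- Under Protocol 7.1.1.1, a reaction during administration leads to discontinuation from the study. If it happens at the second dose, the TEAE leading to withdrawal starts on the omitted date, and withdrawals are one of the three items being split.
- SAP 9.1 imputes some partial start dates to the most recent dosing date. After the second dose that is the Visit 2 date. If imputed dates are used for this sort, those events fall into the gap as well.

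**Working it through.** The plan states no figure to reproduce here. Both rules are logical conditions and can be checked by enumeration.

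**1. Diastolic rule.** Let *b* be baseline (SAP Section 4: last non-missing value before the first dose) and *p* the post-dose value.

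- The rule is *p* − *b* > 10 and *p* < 50. Hence *b* < *p* − 10 < 40.
- In whole mmHg, *p* ≤ 49 and *b* ≤ *p* − 11, so *b* ≤ 38. At the boundary, 38 to 49 is flagged and 39 to 49 is not.
- Falls have *p* − *b* < 0, so none can qualify. Examples not flagged: 75 to 45, 75 to 48, 60 to 40.
- Rises ending at 50 or above fail the second condition. Example not flagged: 80 to 110.
- Take a grid of baselines 30-120 and post-dose values 20-120. For each *p* from 20 to 49, the baselines giving a fall of more than 10 number 120 − (*p* + 11) + 1 = 110 − *p*, running from 90 down to 61. Their sum is 30 × (90 + 61) / 2 = 2,265 pairs, of which 0 are flagged. No pair with baseline 40 or more is flagged either.

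**2. Is the row out of pattern?** These are the Appendix 14.3 criteria that join a direction to a limit:

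| Type | Rows | Count |
|---|---|---|
| Decrease with a lower limit | 6 hematology, potassium, sodium, systolic | 9 |
| Increase with an upper limit | 6 hematology, glucose, bilirubin, ALP, AST, ALT, potassium, sodium | 13 |
| Increase with a lower limit | diastolic | 1 |

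The total is 23, and 22 match.

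**3. How often could the written rule fire?** The documents give no diastolic distribution, so this step rests on an assumption: baseline normal, with mean *m* of 65-80 and SD *s* of 8-12 mmHg. The expected number of 20 subjects with baseline below 40 is 20 × Φ((40 − *m*)/*s*).

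- *m* = 75, *s* = 10: 20 × 0.00023 = 0.005.
- *m* = 65, *s* = 12 (least favourable): 20 × 0.01861 = 0.37.

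A baseline below 40 is necessary but not sufficient for a flag, so these are upper bounds on the expected number of flagged subjects.

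**4. TEAE periods.** SAP Table 8-1 sets the Visit 2 target at Day 43 and EOS 28 days after the second dose, so Day 43 + 28 = Day 71.

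- Period 1, read by date: 1 < *d* < 43, Days 2-42, 41 days.
- Period 2: *d* > 43, Days 44-71, 28 days.
- Covered: 41 + 28 = 69 of 71 days. The uncovered days are 1 and 43, the two dosing days.
- If Day 1 after the dose is read as falling after Visit 1, only Day 43 is uncovered.
- With Visit 2 on Day 50 or Day 57, the result is the same: the Visit 2 day itself is always uncovered.

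With period 1 starting at the first dose and period 2 starting at the second, no start day is left out for any of these Visit 2 dates.

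**The case against.** The best case against is that neither slip removes anything from the report. Diastolic values and changes are summarized and listed for the whole Safety Set, the systolic flag works, and with about 20 subjects a fall would be visible in the listing. Protocol 9.5.4 asks for flagging of laboratory parameters only, so the vital-sign flag is an SAP addition and no protocol commitment is broken. Hypotension as a reaction would also be captured as an adverse event. All of this stands, and it confines the first problem to the flag output.

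The flags also rest on internal guidelines that are not in the documents, so the limit could be the error instead of the direction. That is right: the systolic row makes a decrease the likelier intent, but only the sponsor can confirm it.

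On the TEAE split, Sections 9.4.1 and 9.4.2 are adjacent and their tables are numbered consecutively. They may be meant as dosing days in one and all other days in the other. That is a fair reading, but the SAP does not say so. Its text also gives no dosing-day breakdown by visit for SAEs or withdrawals. Table 14.3.2.1 might include them, but its layout is in specifications kept outside the SAP. Both do appear in the overall tables and listings under 9.4.

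The Day 1 point is weaker than the Visit 2 point. The text refers to Visit 1 without the word date, so Day 1 is ambiguous, while the Visit 2 date is excluded outright.

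**Conclusion.** Both points hold, and both should be fixed. The diastolic criterion can be met only from a baseline below 40 mmHg and never flags a fall. This follows from the inequality alone and needs no assumption; only the estimate of how rarely it would fire (0 to 0.37 of 20 subjects at most) rests on assumed baselines. The by-visit TEAE summary omits the Visit 2 date under any reading, and omits Day 1 as well if the first category is read by date. Its two columns need not add up to the overall TEAE count.

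The reach is limited to the diastolic part of Table 14.3.4.2 and to Table 14.3.2.3. The primary endpoint is unaffected. Because SAP Section 2 gives the SAP precedence over the protocol where their analyses differ, the rules should be expected to be programmed as they stand.

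**What to change.** **Diastolic row.** The sponsor should reconcile the direction and the limit against its internal guidelines and correct Appendix 14.3. A decrease, mirroring the systolic row, is the likely intent of this reporting flag, but the sponsor must confirm it.

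**TEAE periods in 9.4.2.** Define them by recorded dose date and time:

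1. from the start of the first dose to before the start of the second, or to the end of follow-up if no second dose is given;
2. from the start of the second dose to EOS.

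Add a rule for events on the Visit 2 date without a time. Add another for events with no start date, which SAP 9.3 treats as treatment-emergent and which otherwise still have no period. State whether imputed partial dates are used for the sort.

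If 9.4.1 and 9.4.2 are instead meant to be complementary, say so in 9.4.2, and report SAEs and withdrawals on dosing days by visit.

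**Cost.** Wording edits in two places of the SAP, the matching program lines, and the table specifications if they repeat the same rules. No new data are needed, since SAP 9.2 already provides that "The date and time for each dose will be recorded in the CRFs".

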15 ATTACHMENTS

15.1 Table of Contents for Data Display Specifications

Tables		
Number	Title	Population
14.1.1	Summary of Subject Disposition	All Subjects
14.1.2.1	Summary of Subject Demographics and Baseline Characteristics	Safety
14.1.3.1	Medical History by System Organ Class and Preferred Term	Safety
14.1.3.2	Surgical or Procedural History by System Organ Class and Preferred Term	Safety
14.1.4.1	Summary of Prior Medications by Drug Class and Preferred Term	Safety
14.1.4.2	Summary of Concomitant Medications by Drug Class and Preferred Term	Safety
14.1.4.3	Summary of Prior Medications for the Treatment of Systemic Amyloidosis by Drug Class and Preferred Term	Safety
14.1.4.4	Summary of Concomitant Medications for the Treatment of Systemic Amyloidosis by Drug Class and Preferred Term	Safety
14.1.5	Summary of Protocol Deviations	Enrolled
14.1.6	Summary of Treatment Exposure	Safety
14.2.1.1.1	Within Reader Repeatability Coefficients by Reader, Visit, and SUV Metric by Organ	Image Evaluable Set
14.2.1.1.2	Within Reader Repeatability Coefficients by Reader, Visit, and SUV Metric by Organ and Amyloid Type	Image Evaluable Set

Page 33 of 38

14.2.1.2.1	Between Visit Repeatability Coefficients by Reader and SUV Metric by Organ	Image Evaluable Set
14.2.1.2.2	Between Visit Repeatability Coefficients by Reader and SUV Metric by Organ and Amyloid Type	Image Evaluable Set
14.2.1.3	Summary of Repeatability Analysis Results	Image Evaluable Set
14.2.2.1	Among Reader Intraclass Correlation Coefficients by Visit and SUV Metric by Organ	Image Evaluable Set
14.2.2.2	Among Reader Intraclass Correlation Coefficients by Visit and SUV Metric by Organ and Amyloid Type	Image Evaluable Set
14.2.3.1	Summary of Inter-rater Agreement by Visit by Organ	Image Evaluable Set
14.2.3.2	Summary of Intra-rater Agreement by Expert Radiologist by Organ	Image Evaluable Set
14.2.4	Coefficients of Variation by Visit by Organ	Image Evaluable Set
14.3.1.1	Overall Summary of Treatment-Emergent Adverse Events	Safety
14.3.1.2	Treatment-Emergent Adverse Events by System Organ Class and Preferred Term	Safety
14.3.1.3	Treatment-Emergent Adverse Events by System Organ Class, Preferred Term, and CTCAE Grade	Safety
14.3.1.4.1	Treatment-Emergent Adverse Events by System Organ Class, Preferred Term, and Relationship to AT-01	Safety
14.3.1.4.2	Treatment-Emergent Adverse Events by System Organ Class, Preferred Term, and Relationship to KI	Safety

Page **34** of **38**

14.3.1.5	Treatment-Emergent Serious Adverse Events by System Organ Class and Preferred Term	Safety
14.3.1.6	Treatment-Emergent Adverse Events Resulting in Study Withdrawal by System Organ Class and Preferred Term	Safety
14.3.1.7	Treatment-Emergent Adverse Events Resulting in Death by System Organ Class and Preferred Term	Safety
14.3.2.1	Summary of Treatment-Emergent Adverse Events on Day of Dosing by Visit	Safety
14.3.2.2	Treatment-Emergent Adverse Events on Day of Dosing by System Organ Class, Preferred Term, and CTCAE Grade by Visit	Safety
14.3.2.3	Summary of TEAEs by Visit	Safety
14.3.2.4	Summary of Hypersensitivity SMQ TEAEs by System Organ Class and Preferred Term by Visit	Safety
14.3.3.1	Laboratory Results: Chemistry	Safety
14.3.3.2	Laboratory Results: Hematology	Safety
14.3.3.3.1	Laboratory Results: Urine and Biomarker Results	Safety
14.3.3.3.2	Laboratory Results: Biomarker Result Categories	Image Evaluable Set
14.3.3.4	Clinically Significant Changes in Laboratory Values	Safety
14.3.4.1	Vital Sign Results	Safety
14.3.4.2	Clinically Significant Changes in Vital Signs	Safety

Page **35** of **38**

Version Date: 2022-12-16 Version: 2.0

Document Control No.: TMP-SA-008-01 Template Effective Date: 23 Mar 2021

Figures		
Number	Title	Population
14.2.1.1	Between Reader Bland Altman Plots of Difference in SUV metrics vs Average of SUV metrics by Visit and Organ	Image Evaluable
14.2.1.2	Between Reader Bland Altman Plots of Difference in SUV metrics vs Average of SUV metrics by Reader, Visit, and Organ and Amyloid Type	Image Evaluable
14.2.1.3	Between Visit Bland Altman Plots of Difference in SUV metrics vs Average of SUV metrics by Reader and Organ	Image Evaluable
14.2.1.4	Between Visit Bland Altman Plots of Difference in SUV metrics vs Average of SUV metrics by Reader and Organ and Amyloid Type	Image Evaluable
14.2.2	Signal to Noise Ratio vs SUV metrics by Reader, Visit, and Organ	Image Evaluable
14.2.3	Contrast to Noise Ratio vs SUV metrics by Reader, Visit, and Organ	Image Evaluable

Listings		
Number	Title	Population
16.2.1	Subject Disposition	All Subjects
16.2.2	Protocol Deviations	Safety
16.2.3.1	Inclusion/Exclusion Criteria Not Met	All Subjects
16.2.4.1	Demographics and Baseline Characteristics	Safety
16.2.4.2	Baseline Disease Characteristics	Safety
16.2.4.3.1	Medical History	Safety
16.2.4.3.2	Surgical or Procedural History	Safety
16.2.4.4	Prior and Concomitant Medications	Safety
16.2.4.5	Prior and Concomitant Medications - Amyloid	Safety
16.2.4.6	Pregnancy Test Results	Safety
16.2.5.1	¹²⁴ I-AT-01 Administration	Safety
16.2.5.2	Potassium Iodide Administration	Safety
16.2.6	Imaging Results	Image Evaluable
16.2.7.1	Adverse Events by Subject, System Organ Class, and Preferred Term	Safety
16.2.7.2	Treatment-Emergent Adverse Events on Day of Dosing by Subject, System Organ Class, and Preferred Term	Safety
16.2.7.3	Treatment-Emergent Adverse Events on Day of Dosing Reported on the AT01 Administration CRF	Safety
16.2.8.1	Laboratory: Chemistry	Safety
16.2.8.2	Laboratory: Hematology	Safety

Page **37** of **38**

Version Date: 2022-12-16 Version: 2.0

Document Control No.: TMP-SA-008-01 Template Effective Date: 23 Mar 2021

Attralus, Inc.

 $Statistical\ Analysis\ Plan-AT01-001$

16.2.8.3	Laboratory: Urine and Biomarker Results	Safety
16.2.8.4	Vital Signs	Safety
